## **Introduction**

Psychedelics are again at the forefront of psychiatric research as the search intensifies for more effective interventions to address emotional disturbances beyond conventional treatment (Carhart-Harris et al., 2017). Several psychedelics have been identified as having breakthrough potential when administered in combination with psychotherapy, including ketamine-assisted psychotherapy (KAP) (Ezquerra-Romano et al., 2018; Greenway et al., 2020; Luoma et al., 2020; Reiff et al., 2020). Overall the clinical trials evidence for psychedelic-assisted therapies is early (Wheeler et al., 2020) and multiple randomised controlled trials (RCTs) are underway around the world (see [clinicaltrials.gov](https://clinicaltrials.gov)).

Although RCTs can best answer questions of safety and efficacy, there remains an urgent need to clarify the real-world effectiveness of psychedelic-assisted therapies. Field Trip Health administers KAP for adult clients coping with mental health. KAP consists of 4-6 guided ketamine sessions with psychotherapy-only visits after dose 1 and 2 and then after every 2 subsequent doses.

This proposal is for a retrospective intervention-only effectiveness trial based on review of Field Trip Health patient outcomes across its North American centres. Its objectives are: 1. to characterise baseline patient characteristics; 2. to identify treatment variation; 3. to determine the trajectory of mental health outcomes; and 4. to estimate effect sizes associated with treatment. We hypothesized sustained reductions in depression, anxiety, and post traumatic stress over time.

## **Method**

### *Sample and Procedure*

Patients treated at Field Trip Health are initially assessed by a psychiatrist or a psychiatric nurse practitioner to determine appropriateness for treatment. Eligibility criteria are as follows.

- Inclusion Criteria:
  - Written informed consent
  - Over the age of 18
  - Should be psychologically and medically cleared by a psychiatrist, family physician, or treatment team
  - Diagnosed with Major Depressive Disorder (MDD), Bipolar Depression, Generalized Anxiety Disorder, Obsessive Compulsive Disorder (OCD), and Eating

Disorder by a licensed healthcare practitioner (including Field Trip Consultants)

- A significant history of trauma and/or formal diagnosis of PTSD as per the Diagnostic and Statistical Manual of Mental Disorders 5 (DSM 5)
- Individuals who have received Electroconvulsive Therapy (ECT) or other neuromodulatory treatments like Transcranial Magnetic Stimulation (TMS)
- Individuals reporting suicidal ideation may be included, as suicidal ideation is a symptom of a Major Depressive Episode (MDE)

● Exclusion Criteria:

- Individuals who are unable to consent to the treatment
- Pregnant women and nursing mothers
  - Note that Post Partum Depression (PPD) can be considered on a case-by-case basis in consultation with the National Medical Director.
- There is a relative (not absolute) contraindication for individuals with a Body Mass Index (BMI) of above 35. These clients must be given thorough consideration by the medical team.
- Any individual who has met DSM 5 criteria for a Substance Use Disorder in the past 3 months.
  - Note that patients with alcohol, opioid, benzodiazepine, cocaine, and amphetamine use disorders need to go through detox (for alcohol/benzodiazepines) and be sober for 4 weeks.
  - Note that mild active alcohol, cocaine, and cannabis use can be considered on a case-by-case basis at the comfort level of the treatment team if the client has demonstrated abstaining or significant reduction of use prior to starting treatment.
- Daily use of moderate to high doses of benzodiazepines
- Individuals who are experiencing psychotic symptoms as part of an MDE (mood congruent/ mood incongruent)
- Psychosis: Schizophrenia, Schizoaffective disorder, Bipolar 1 with psychotic features during mania
- Active Mania: Bipolar 1 (chronic non-disruptive hypomania is an exception at the discretion of the consultant)
- Borderline Personality Disorder
- Uncontrolled medical disorders
- Physical conditions with negative interaction with ketamine (e.g., metabolic blood disorder)
- Individuals with symptomatic acute brain injury within 90 days of serious injury
- Individuals diagnosed with moderate to severe sleep apnea
- Individuals who are unable to identify a person or service to assure their safe transport to home post treatment

As a part of the intake process of the program, patients provide written informed consent and complete questionnaires via a Health Insurance Portability and Accountability Act (HIPAA) and Personal Health Information Protection Act (PHIPA) compliant Electronic Medical Records (EMR) system.

Questions include information on demographics, past medical history as well as standardized mental health questionnaires. Patients are also encouraged to complete these scales at several additional points during the treatment program and then at 1, 3, and 6 months after program completion. Data will be reviewed from patients who were treated with KAP across 11 Field Trip Health locations across North America from March 2020 to June 2022.

These locations include:

- 1) Toronto, ON, Canada
- 2) Vancouver, BC, Canada
- 3) Fredericton, NB, Canada
- 4) New York City, NY, USA
- 5) Atlanta, GA, USA
- 6) Chicago, IL, USA
- 7) Houston, TX, USA
- 8) Seattle, WA, USA
- 9) Santa Monica, CA, USA
- 10) San Diego, CA, USA
- 11) Washington, DC, USA

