#### *Measures of Interest*

- a) Demographic variables, including age and gender.
- b) Medical variables, including main diagnosis and length of illness.
- c) Treatment-related variables, including number and timing of ketamine sessions, number and timing of psychotherapeutic sessions, and site.
- d) Primary clinical outcomes were:

- i. Change in depression at 3 months relative to baseline assessed by 9-item Patient Health Questionnaire (PHQ-9) (Kroenke et al., 2001);
- ii. Change in anxiety at 3 months relative to baseline assessed by 7-item Generalized Anxiety Disorder measure (GAD-7) (Spitzer et al., 2006);
- iii. Change in post traumatic stress at 3 months relative to baseline by 6-item Post Traumatic Stress Disorder (PTSD) Checklist (PCL-6) (Lang & Stein., 2005).

e) Secondary clinical outcomes were:

- i. Change in depression at 1 month relative to baseline assessed by PHQ-9;
- ii. Change in anxiety at 1 month relative to baseline assessed by GAD-7;
- iii. Change in post traumatic stress at 1 month relative to baseline assessed by PCL-6;
- iv. Change in depression at 6 months relative to baseline assessed by PHQ-9;
- v. Change in anxiety at 6 months relative to baseline assessed by GAD-7;
- vi. Change in post traumatic stress at 6 months relative to baseline assessed by PCL-6.

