### **Impact**

Field Trip Health's large-scale dataset may provide real-world benchmarks concerning the sustained benefits of ketamine-assisted psychotherapy. Given the scale of interest by policymakers, clinicians, researchers, and patients, these findings may be suitable for publication in a high impact journal, offering scientific validation of Field Trip Health's therapeutic product.

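### Bipolar and suicidal patients can be included, but no manic switch, adverse event, admission or death is listed or given an analysis rule, so some bad outcomes may appear only as missing scores and harms go uncounted

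*Combined protocol and SAP*

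**What the plan says.** Sample and Procedure takes patients "Diagnosed with Major Depressive Disorder (MDD), Bipolar Depression, Generalized Anxiety Disorder" and further diagnoses. It excludes active mania, but "chronic non-disruptive hypomania is an exception at the discretion of the consultant". Patients reporting suicidal ideation may also be treated.

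Measures of Interest names three kinds of explanatory variable besides the outcomes. Apart from demographics these are "Medical variables, including main diagnosis and length of illness" and "Treatment-related variables, including number and timing of ketamine sessions, number and timing of psychotherapeutic sessions, and site". The outcomes are changes in PHQ-9, GAD-7 and PCL-6 at 1, 3 and 6 months, with 3 months primary. No mania measure, adverse event, reason for stopping, admission, suicide attempt or death is named.

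Under Data Handling, a data administrator collates and de-identifies the assessments for the research team, and the full clinical data stay with internal clinical staff. Statistical Analysis specifies intention to treat and mixed linear models. It will describe how much is missing at each occasion but does not mention the reasons. Multiple imputation and the testing of predictors are optional. Impact presents the findings as "real-world benchmarks concerning the sustained benefits of ketamine-assisted psychotherapy" and as validation of the clinic's product.

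**The concern.** The entry criteria make serious psychiatric events foreseeable in this sample, yet the listed data would not show them for what they are. Three consequences follow.

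- **Missing scores.** A death, or an admission after which the patient stops answering, leaves only absent questionnaires. A mixed model assumes that the observed data explain the absence, so it implicitly gives these patients the course of others with similar earlier scores. Multiple imputation in its usual form makes the same assumption and would not test it.
- **Manic switch.** No listed scale measures mania. If a switch lowers the PHQ-9, it is scored as improvement and may count as a case reduction or as reaching the minimal clinically important difference (MCID).
- **No count of harms.** The study would offer benchmarks of benefit with no event counts beside them. There is no control arm, so recording such events is one of the few checks available.

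The research team receives a prepared dataset, so an item not specified before extraction may never reach the analysts.

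**Working it through.** **Inputs.** The documents give no sample size, bipolar share, switch rate, event rate, dropout rate or standard deviation, so there is no figure of the plan's to reproduce. The check is first a reading of the variable list, then an illustration on assumed rates.

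**Step 1: what each event would look like in the listed data.**

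- Stopping early: visible from the number and timing of sessions; the reason is not listed.
- Stopping or admission, but the patient still answers: the reported score is kept under intention to treat.
- Admission without further answers, or death: missing scores only.
- Hypomania or mania: nothing, except whatever happens to the PHQ-9, GAD-7 and PCL-6 totals.
- Adverse event at a session: nothing.

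**Step 2: effect on the standardised mean change.** Let d be the effect in patients without an event, q the share with an unrecorded event and no score, and w the worsening assigned to them in SD units. If the model in effect gives them d, the comparison is with

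d_all = (1 − q) × d − q × w.

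| q | d = 0.8, w = 0 | d = 0.8, w = 0.5 | d = 0.5, w = 0 |
|---|---|---|---|
| 2% | 0.784 | 0.774 | 0.490 |
| 5% | 0.760 | 0.735 | 0.475 |
| 10% | 0.720 | 0.670 | 0.450 |
| 20% | 0.640 | 0.540 | 0.400 |

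For example, 0.95 × 0.8 − 0.05 × 0.5 = 0.735. The values 0.8 and 0.5 are the conventional benchmarks cited in Statistical Analysis, not effects that the plan assumes.

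**Step 3: effect on the responder share.** The plan does not say how patients without a score enter the case and MCID proportions. If they are left out and the share among the rest is r, counting them as failures gives r × (1 − q). With an assumed r = 60%, this is 58.8%, 57%, 54% and 48% for q = 2%, 5%, 10% and 20%.

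**Step 4: manic switch.** The share of the cohort affected is the bipolar share times the switch rate. With an assumed bipolar share of 5% to 20% and switch rate of 2% to 10%, it runs from 0.05 × 0.02 = 0.1% to 0.20 × 0.10 = 2%. Within the bipolar group it is the switch rate itself, 2% to 10%. For given rates these are upper bounds: every switch would have to coincide with an endpoint and lower the PHQ-9 past the threshold.

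On these inputs, events hidden behind missing scores could move the pooled result more than misread switches.

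**The case against.** The best defence is scope. The Introduction says that randomised trials best answer safety questions, and none of its four objectives concerns safety. That fairly explains why there is no safety endpoint. It does not settle how a switch, admission or death enters the effectiveness estimate.

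Several stronger readings are tempting, and the documents do not support them.

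- *A patient who stops treatment is only a missing score.* Session counts and timing are listed, treatment variation is an objective, and a patient who stops but answers keeps the real score. Only the reason is lost.
- *No event data will be extracted.* The demographic, medical and treatment lists are worded as open, so the most that can be said is that none is listed.
- *The study can show only benefit.* All three scales can worsen, and the trajectories would show it. Event reporting is what is absent.
- *A manic switch is scored as improvement.* Nothing in the documents says that a switch lowers the PHQ-9. It is a possibility.

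Two practical objections also stand. Counting every admitted patient as not improved would replace an observed score with a composite, when keeping the reported score is a legitimate choice. And follow-up after the program is described only as questionnaires that patients are encouraged to complete, so the clinic record may miss outside admissions, attempts and deaths.

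**Conclusion.** The concern holds in a limited form. The plan admits patients in whom these events are foreseeable, lists none of the events and has no rule for them. A death or a non-answering admission would therefore look like ordinary missing data, and a switch might be read as improvement.

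The effect on the primary mean changes is probably small: at q = 2% to 5%, d = 0.8 falls by 0.016 to 0.040 with no change assigned, or by 0.026 to 0.065 with worsening of 0.5 SD. It would matter more only at event shares of 10% to 20%. All of these rates are assumptions. The documents do not support a claim that the primary estimates are materially biased.

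What does not depend on any rate is that the listed variables yield no count of harms to set beside the claimed benefits. This is a worthwhile and inexpensive improvement, not a flaw that invalidates the analysis.

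**What to change.** In Measures of Interest, add the following from the existing medical record, with dates: clinician-recorded hypomania, mania or psychosis; adverse events at sessions; reason for stopping; psychiatric admission; suicide attempt; and death.

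In Statistical Analysis:

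- Tabulate these events and the reasons for missing scores beside the effect sizes.
- Show PHQ-9 change separately for patients whose main diagnosis is bipolar. Main diagnosis is already listed, but analysis by it is optional at present.
- As a sensitivity analysis only, count a patient with a recorded switch, psychiatric admission or death before the endpoint as not improved in the case and MCID proportions.
- State that events after program completion or outside the clinic may be under-recorded, so the counts are minimums. If the record lacks a field, report that as a limitation.

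The cost is extra extraction work for the data administrator and possibly a slightly lower responder share in the sensitivity analysis. The review is retrospective, so no patient procedure is added and no clinical rule changes.

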#### *Data Handling*

The full clinical dataset is managed by a data administrator who will collate the assessments and de-identify the data so that no personal identifying information remains. This de-identified dataset will then be analysed by research team members. Full clinical data is held on encrypted servers with password protection and accessible only to internal clinical staff. Only research team members will be allowed access to the de-identified research dataset which will also be kept on password protected servers and computers.

Should a data breach or leak should occur, our data mitigation plan is to contact Veritas Internal Review Board (IRB) to inform them of the breach, assess the extent of the breach, and determine what steps can be taken to address the situation. We will also plan to inform affected clients of the event and the actions being taken.

#### *Measures of Interest*

- a) Demographic variables, including age and gender.
- b) Medical variables, including main diagnosis and length of illness.
- c) Treatment-related variables, including number and timing of ketamine sessions, number and timing of psychotherapeutic sessions, and site.
- d) Primary clinical outcomes were:

- i. Change in depression at 3 months relative to baseline assessed by 9-item Patient Health Questionnaire (PHQ-9) (Kroenke et al., 2001);
- ii. Change in anxiety at 3 months relative to baseline assessed by 7-item Generalized Anxiety Disorder measure (GAD-7) (Spitzer et al., 2006);
- iii. Change in post traumatic stress at 3 months relative to baseline by 6-item Post Traumatic Stress Disorder (PTSD) Checklist (PCL-6) (Lang & Stein., 2005).

e) Secondary clinical outcomes were:

- i. Change in depression at 1 month relative to baseline assessed by PHQ-9;
- ii. Change in anxiety at 1 month relative to baseline assessed by GAD-7;
- iii. Change in post traumatic stress at 1 month relative to baseline assessed by PCL-6;
- iv. Change in depression at 6 months relative to baseline assessed by PHQ-9;
- v. Change in anxiety at 6 months relative to baseline assessed by GAD-7;
- vi. Change in post traumatic stress at 6 months relative to baseline assessed by PCL-6.

### *Statistical Analysis*

Descriptive statistics will characterize the sample. This will include an analysis of variations in treatment delivery and the extent of missing values across measurement occasions. Analysis of treatment effects is by intention to treat. The main analysis will be mixed linear models to plot the normative patient trajectories or growth curves for each outcome, producing estimates of mean changes at each endpoint (i.e. 1, 3, and 6 months) relative to baseline (Bell et al., 2013). Cohen's  $d$  will be our standardised measure of effect size. By convention, values of  $d = 0.2, 0.5,$  and  $0.8$  correspond to small, medium, and large effects.

Secondary analyses will include evaluating case reductions (identified by validated cut-off values relevant to each measure) and proportions of patients reporting minimal clinically important differences (MCIDs) at each endpoint relative to baseline. Additional analyses may include a sensitivity analysis involving multiple imputation of missing values to examine the stability of estimates. Demographic, medical, and treatment-related variables may be tested as predictive factors.

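### The main mixed model pre-specifies no intake covariate beyond the baseline score, so the 3-month change shifts if a recorded variable is related both to voluntary return and to change

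*Combined protocol and SAP*

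**What the plan says.** All references are to the combined protocol and SAP.

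- **Main model (Statistical Analysis).** "The main analysis will be mixed linear models to plot the normative patient trajectories or growth curves for each outcome". The section names no covariate for this model. The baseline score enters as the reference for change, since the stated output of the model is "producing estimates of mean changes at each endpoint (i.e. 1, 3, and 6 months) relative to baseline".
- **Population (Statistical Analysis).** "Analysis of treatment effects is by intention to treat".
- **Recorded variables (Measures of Interest).** Age and gender are listed, then "Medical variables, including main diagnosis and length of illness", then treatment variables and site. The primary outcomes are the 3-month changes in PHQ-9, GAD-7 and PCL-6.
- **Planned use of those variables (Statistical Analysis).** "Demographic, medical, and treatment-related variables may be tested as predictive factors". This is optional and is not tied to the main estimate. Multiple imputation is also optional, with no imputation variables named.
- **Return of the scales (Sample and Procedure).** "Patients are also encouraged to complete these scales at several additional points during the treatment program", and again at the three follow-up times. No completion rate is given. The plan describes how much is missing at each occasion, but not who is missing.

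**The concern.** A likelihood-based mixed model with time alone gives a valid mean change if missingness depends only on scores that were observed. Suppose return also depends on, say, main diagnosis, and patients with different diagnoses change by different amounts. The assumption then fails, and it fails because of a variable that the study records.

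The eligibility criteria admit several diagnoses (depressive, bipolar, anxiety, obsessive-compulsive, eating and trauma-related), and all patients are assessed on the same three scales. Different mean change by diagnosis is therefore plausible, though the documents do not show it.

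What is at stake is whom the three primary estimates describe. The plan claims intention to treat, and its Impact section offers the results as real-world benchmarks. Both imply all treated patients. A time-only model can instead describe a population partly re-weighted by who answers. The error does not shrink as the sample grows. Silence about covariates in a retrospective single-arm study also leaves the choice open until the results have been seen.

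**Working it through.** **Nothing to reproduce.** The documents state no sample size, SD, return rate or subgroup change. Every input below is an assumption.

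**Step 1: the shift if the estimate moved all the way to the returners' mix.** With group shares p, 3-month return rates r and true changes Δ:

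- true mean = Σ pΔ
- returners' mean = Σ p·r·Δ / Σ p·r

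For scenario (a), with groups 60/40, changes −8 and −4, and return 40% and 15%:

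- true mean = 0.6(−8) + 0.4(−4) = −6.4
- returners' mean = [0.24(−8) + 0.06(−4)] / 0.30 = −2.16 / 0.30 = −7.20

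**Step 2: what the mixed model gives.** Simulation inputs: n = 1000, baseline 15, SD 5 to 6, time as categories (baseline, 1, 3 and 6 months), unstructured covariance. Monte Carlo error is about 0.05.

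| Scenario (groups 60/40) | Truth | Returners' mean | Time-only model | Shift | Covariate by visit, averaged over full cohort |
|---|---|---|---|---|---|
| (a) −8/−4, return 40/15% | −6.4 | −7.20 | −7.03 | 0.63 | −6.37 |
| (b) −8/−4, return 45/30% | −6.4 | −6.77 | −6.66 | 0.26 | −6.40 |
| (c) −7/−5, return 35/20% | −6.2 | −6.45 | −6.41 | 0.21 | −6.23 |
| (a) with return reversed, 15/40% | −6.4 | −5.44 | −5.71 | 0.69, towards too little change | not tabulated |

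The adjusted figure in (a) uses all four covariates by visit; those in (b) and (c) use diagnosis by visit. In (a) the time-only model moves 0.63 of the possible 0.80 points, so the shift is partial. With equal return in the two groups the models agree.

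**Step 3: which conditions are needed.** A second design used two equal groups, SD 5.5, correlation 0.5 and four runs of 20,000 patients. Ranges cover return drawn separately at each visit and permanent dropout.

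| Case | Truth | Time-only model |
|---|---|---|
| Return 30/60%, same change, same baseline | −5.00 | −5.01 to −5.02 |
| Return 30/60%, same change, baselines 3 points apart | −5.00 | −4.80 to −4.83 |
| Return equal, change −3/−6 | −4.50 | −4.53 |
| Return 30/60%, change −3/−6 | −4.50 | −4.93 to −5.03 |

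For the last row the full shift is [0.60/(0.30 + 0.60) − 0.5] × 3 = 0.50 points. Under permanent dropout nearly all of it appears, because the non-returners leave few later scores. Harsher inputs give more: with changes −2/−7 and return 20/60% the model gave −5.51 to −5.76 against −4.50, a shift of 1.01 to 1.26.

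**Step 4: which adjustment works.** In the 30/60%, −3/−6 case the full-data value in the same runs was −4.52 to −4.55.

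- Group as a main effect only: −4.84 to −4.93, so most of the drift remains.
- Group by time, averaged over the full intake mix: −4.55.

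**Step 5: in-treatment scores.** Adding a near-complete in-treatment score to that case gave −4.76 to −4.90. This removes about 0.1 to 0.25 of the 0.5 points.

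**Step 6: scale.** At SD 5.5, shifts of 0.2 and 0.7 points are 0.2/5.5 = 0.04 and 0.7/5.5 = 0.13 in units of d. In (a) the SD of the estimate is 0.32 without covariates and 0.35 with them, so the shift there is 0.63/0.32, about two SDs of the estimate.

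**The case against.** The strongest reply is that the plan is silent rather than wrong. It does not specify a time-only model, it already uses the baseline score, and it allows for predictor testing, multiple imputation and a description of missing values. The shift is hypothetical, and at 0.04 to 0.13 in d it lies below the 0.2 that the plan itself calls small. Retrospective covariates may be incomplete, and a standard mixed model drops patients who lack one, which would damage the intention-to-treat set.

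Part of this stands. The size in this study is unknown, and incomplete covariates must be handled in the fix. The optional analyses could carry these variables, but nothing commits the plan to run them or to include the variables. A shift below a small d can still matter against the precision of the estimate, as scenario (a) shows.

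A reader might infer more than the documents support:

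- **That voluntary return, or return differing by diagnosis, is enough to cause bias.** It is not. Change, or more weakly baseline level, must differ too.
- **That the bias flatters the treatment.** The documents do not say which patients return, and reversing the rates reverses the sign.
- **That a missing 3-month score is informed only by earlier scores.** The model uses all observed scores, including those at 6 months.
- **That the listed variables are complete for every patient.** They are listed as measures of interest, and nothing is said about completeness.

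**Conclusion.** The concern holds in a limited form. The plan pre-specifies no intake covariate beyond the baseline score for the main model. It lists variables that could correct one source of bias but gives them only an optional role. If such a variable is related both to return and to change (or, more weakly, to baseline level), the 3-month estimate shifts towards the returners' mix by an amount and in a direction not known in advance.

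On the assumed inputs of the 60/40 scenarios the shift is about 0.2 to 0.7 points, with larger values under more extreme contrasts. It is zero if return is unrelated to these variables, and smaller if in-treatment scores enter the model. The documents do not show that the shift is present in this study.

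Nor should a reader infer that adjustment would make the estimates unbiased. It deals only with the part of missingness explained by the recorded variables. Return that depends on unseen scores or unrecorded factors is untouched. The change is worth making because it uses variables the plan already lists, at little cost.

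**What to change.** In the Statistical Analysis section:

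1. Add age, gender, main diagnosis (rare groups pooled) and length of illness to the main model, each with a visit interaction. Main effects alone are not sufficient.
2. Report the 1-, 3- and 6-month changes averaged over the intake distribution of all treated patients, not of returners and not with equal weight per category.
3. Keep patients with a missing covariate in the analysis, by a missing category or by imputation, and say which.
4. Use the same variables in any multiple imputation.
5. State whether site, which is also recorded, is included, and why.
6. Tabulate intake characteristics of returners and non-returners at each visit, so that readers can judge whether return is related to them.

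The cost is a few lines of text, no new data collection, some work on incomplete covariates, and slightly wider intervals (SD of the estimate about 0.35 against 0.32 in scenario (a)).

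### The only missing-data sensitivity analysis is an optional, unspecified multiple imputation, which in standard form would not show how far the 3-month changes depend on non-response linked to the unseen score

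*Combined protocol and SAP*

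**What the plan says.** The combined protocol and SAP collects follow-up scores by voluntary self-report. Under Sample and Procedure, patients are "encouraged to complete these scales at several additional points during the treatment program and then at 1, 3, and 6 months after program completion". The three primary outcomes are the 3-month changes in PHQ-9, GAD-7 and PCL-6 (Measures of Interest).

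The Statistical Analysis section makes mixed linear models (growth curves) the main analysis, "producing estimates of mean changes at each endpoint (i.e. 1, 3, and 6 months) relative to baseline". It also states: "Analysis of treatment effects is by intention to treat". On missing data it makes one firm commitment, to describe "the extent of missing values across measurement occasions", and one optional one: "Additional analyses may include a sensitivity analysis involving multiple imputation of missing values to examine the stability of estimates". No other missing-data sensitivity analysis appears in the document.

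The design is stated in the Introduction: "This proposal is for a retrospective intervention-only effectiveness trial". The Impact section says the dataset may provide "real-world benchmarks concerning the sustained benefits of ketamine-assisted psychotherapy".

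**The concern.** A patient's decision to return a 3-month questionnaire may depend on how that patient feels at 3 months. If those doing badly stop answering, improvement is overstated; if those who have recovered stop answering, it is understated. With no comparison arm, such bias passes straight into the mean change and into d.

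The planned check may be unable to reveal it. A likelihood-based mixed model and a standard multiple imputation rest on the same kind of assumption: given the variables used, the unseen score itself plays no part in whether it is missing. With the same variables the two are expected to agree, and that agreement could be reported as stability around a biased figure. Describing how much is missing shows the scope for bias but not its possible effect on the estimate.

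**Working it through.** The documents give no response rate, SD, correlation or expected effect. There is no stated figure to reproduce, and every input below is an assumption.

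**1. Would standard imputation reveal the problem?** Assumed simulation: SD 5; baseline mean 15, later means 10.5; correlation 0.5 between baseline and each later score, 0.7 for months 1–3 and 3–6, and 0.6 for months 1–6; in-treatment score correlated 0.70, 0.65 and 0.60 with months 1, 3 and 6; 50% responding at each follow-up. The mixed model is maximum likelihood with unstructured covariance and categorical time, on baseline and months 1, 3 and 6. Entries are the 3-month change in points.

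| Response depends on | True | Mixed model | Imputation, same visits | Imputation plus in-treatment score |
|---|---|---|---|---|
| Baseline only | -4.50 | -4.50 | not run | -4.50 |
| In-treatment score (log-odds 1.0 per SD) | -4.50 | -5.05 | not run | -4.48 |
| Unseen score, worse patients answer less (log-odds 0.5 per SD) | -4.50 | -5.20 | -5.20 | -5.07 |
| Unseen score, direction reversed | -4.48 | -3.81 | -3.81 | -3.95 |

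In rows 1 and 2, imputation with the extra score recovers the truth. In rows 3 and 4, imputation on the same visits matches the mixed model and both are wrong; the extra score reduces the error but does not expose it. A second simulation (correlation 0.4 between baseline and follow-up, 0.6 among follow-ups; log-odds 1 per SD on the unseen score) had the two methods within 0.01 SD of each other, while both overstated improvement by 0.17, 0.31 and about 0.48 SD at 30%, 50% and 70% missing.

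**2. What would a shift do to d?** Let f be the fraction missing at 3 months and k the amount, in baseline SDs, by which non-responders are worse than missing-at-random predicts. Take d as mean improvement divided by baseline SD (the plan names no denominator). For a mean change, or a model with categorical time:

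shifted d = missing-at-random d - f × k.

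For k = 0.5 the movement is 0.3 × 0.5 = 0.15, 0.5 × 0.5 = 0.25 and 0.7 × 0.5 = 0.35. A negative k moves d up by the same amounts.

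**3. How wide must the range of shifts be?** The tipping value is k = (d - threshold) / f. Assume a missing-at-random change of 5 points and baseline SD 5.5, so d = 5/5.5 = 0.909:

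| d falls to | 30% missing | 50% missing | 70% missing |
|---|---|---|---|
| 0.8 | 0.36 | 0.22 | 0.16 |
| 0.5 | 1.36 | 0.82 | 0.58 |
| 0.2 | 2.36 | 1.42 | 1.01 |
| 0 | 3.03 | 1.82 | 1.30 |

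The first row depends heavily on the assumed d lying just above 0.8: at d = 1.1 it becomes 0.30/0.3 = 1.00, 0.30/0.5 = 0.60 and 0.30/0.7 = 0.43. A range that stopped at +1.0 SD would miss seven of the twelve entries in the table. For comparison, non-responders returning to their baseline mean gives d = 0.909 × (1 - f) = 0.64, 0.45 and 0.27.

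**4. Does the analysis model matter?** With complete balanced data at 0, 1, 3 and 6 months, shift only the 3-month scores by one unit. With categorical time, 100% of the shift reaches the 3-month change. For a straight line, the mean time is 2.5, the sum of squared deviations is 21 and the 3-month deviation is 0.5, so the fitted 3-month change moves by 3 × 0.5/21 = 0.07, or 7%. Using log(1 + time), it moves by 1.386 × 0.380/2.138 = 0.25, or 25%. A restrictive growth curve would therefore dilute the shift and could itself suggest false stability.

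**The case against.** The strongest reply has four parts.

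- **The plan does not exclude in-treatment scores from the main model.** The months it lists are the endpoints to be estimated, not the data entered. This stands. A model that already used those scores could have smaller errors than the mixed-model column above, and a reader should not infer that the plan leaves them out.
- **Imputation can do real good.** This also stands: row 2 of the first table shows it. But adding predictors makes the assumption more plausible without testing departures from it.
- **The optional wording could cover a shifted imputation.** It could, but nothing in the text describes or commits to one.
- **The figures are chosen inputs, and one assumed scale stands in for three outcomes.** True. They show mechanism and scale only.

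A reader might also infer that the reported improvement will be overstated. The documents do not support that: they give no response rates or reasons for non-response, and the opposite direction is equally open. Nor do they show that the mixed model is the wrong main analysis. Two further readings are inferences: that estimation is likelihood-based, and that intention to treat, which the plan does not define for a single-arm review, covers treated patients who never return a 3-month scale.

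**Conclusion.** The concern holds in a limited form. The sole missing-data sensitivity analysis is optional and unspecified, and in standard form it would not show how far the three primary 3-month changes depend on non-response linked to the unseen score. This rests on the main model being likelihood-based and the imputation being of the usual missing-at-random kind. The size and direction of any bias in this study are unknown. The general scale is that d moves by the fraction missing times the departure in baseline SDs, provided the change is estimated with categorical time. The main analysis can stand; what it lacks is a committed examination of its key untestable assumption. No analysis of the observed data can establish whether that assumption is true, but a shift analysis can show how strong a departure would have to be to alter the conclusion.

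**What to change.** Replace the optional sentence with a committed analysis for each of the three primary outcomes:

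1. Impute missing 1-, 3- and 6-month scores from all available scores, including in-treatment scores, and from the demographic, medical and treatment variables under Measures of Interest (the last being "number and timing of ketamine sessions, number and timing of psychotherapeutic sessions, and site"). Compare responders with non-responders on these. State the missing-data assumption of the main model and which visits enter it.
2. Shift the imputed 3-month scores by amounts fixed in advance in baseline-SD units, in both directions. Add a scenario in which non-responders' mean returns to baseline. State whether imputed 1- and 6-month scores are shifted too.
3. Estimate the 3-month change and d, with intervals and a stated denominator for d, from the completed data as the mean change or with time as categories, not through a straight-line or other restrictive growth curve.
4. Report the shifts at which d falls below the plan's own 0.8, 0.5 and 0.2 and at which the change is no longer distinguishable from zero. Extend the range or solve for these values directly rather than stopping at +1.0 SD. State them beside any claim of sustained benefit.

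This is a cheap improvement: SAP wording and extra runs on data already held. Eight shifts plus the return-to-baseline scenario, for three outcomes, would be 9 × 3 = 27 analyses. The downsides are that the range of shifts is a judgement to be made before outcomes are analysed, and that less favourable figures may stand beside the main estimate.
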